To estimate duration of erythroid response among responders treated with EPO alone	Duration of erythroid response is defined as the time from onset of the first response to progression/relapse (decrease in Hb \geq 1.5 g/dL from Hb value at response) among responders treated with EPO alone within the whole 24 weeks period	Refer to Section 10.5.7

Objective	Endpoint	Analysis
To estimate duration of erythroid response among responders treated with DFX+EPO	Duration of erythroid response is defined as the time from onset of the first response to progression/relapse (decrease in Hb \geq 1.5 g/dL from Hb value at response) among patients randomized to EPO+DFX up to week 24 and for patients switched from EPO to DFX+EPO from week 13 to week 24	Refer to Section 10.5.8
To evaluate tolerability and safety of the combination	Incidence of adverse events (AEs) overall and by severity, and serious adverse events (SAEs).	Refer to Section 10.5.11
To assess iron parameters in patients randomized to EPO alone, DFX+EPO and in patients randomized to EPO alone and switched to DFX+EPO after 12 weeks	Change in SF from baseline to every visit in patients throughout in the combination arm, throughout in the EPO arm and switched from EPO arm to EPO+DFX after 12 weeks	Refer to Section 10.5.9
To assess Hb parameters in patients randomized to EPO alone, DFX+EPO and in patients randomized to EPO alone and switched to DFX+EPO after 12 weeks	Change in Hb from baseline to every visit in patients throughout in the combination arm, throughout in the EPO arm and switched from EPO arm to DFX+EPO after 12 weeks	Refer to Section 10.5.10
Supportive		
To assess the effect of treatment with DFX+EPO and EPO alone on hematologic improvement within 24 weeks of treatment	Proportion of patients achieving a hematologic improvement (improvement of neutropenia and thrombocytopenia) within 24 weeks of treatment with DFX+EPO and EPO alone	Refer to Section 10.5.1
To assess the effect of treatment with DFX+EPO and EPO alone on total hematological response within 24 weeks of treatment	Proportion of patients achieving a hematological response (increase in Hb, improvement of neutropenia and thrombocytopenia) according to modified IWG 2006 criteria and patients achieving a hematologic improvement (improvement of neutropenia and thrombocytopenia) within 24 weeks of treatment with DFX+EPO and EPO alone	Refer to Section 10.5.1

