6.1.4 Treatment duration

The whole treatment period will last 24 week. The primary objective (erythroid response according to IWG criteria: Hb increase ≥ 1.5 g/dL) will be assessed by 12 weeks of treatment. At any time, if Hb ≥ 12 , EPO will be stopped until the end of study. These patients will be considered as responders.

By 24 weeks, patients initially assigned to the combination therapy who showed Hb increase ≥ 1 g/dL by week 12 will be assessed for full hematological response according IWG criteria (Erythroid response: Hb increase from baseline ≥ 1.5 g/dL; Neutrophil response: increase from baseline of $\geq 100\%$ and $> 0.5 \times 10^9/L$; Platelet response: increase from baseline of $\geq 30 \times 10^9/L$).

If after 12 weeks of treatment with EPO alone, Hb increase is < 1 g/dL and total Hb is < 12 g/dL, the patient will switch to the combination therapy with EPO and DFX for the remaining 12 weeks and will be assessed for erythroid response by 24 weeks. If after 12 weeks of treatment with EPO in combination with DFX, Hb increase is < 1 g/dL and total Hb is < 12 g/dL, the patient will be discontinued from the study.

Subjects need to be discontinued from the study if at least one of the following occurs:

- $\geq 50\%$ decrement from maximum response levels in granulocytes or platelets
- Reduction of Hb level ≥ 1.5 g/dL compared to best response
- Patient requiring blood transfusion at any time

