10.5.7 To estimate duration of erythroid response among responders treated with EPO alone

Descriptive statistics will be provided for responder patients for rate of relapse (decrease in Hb ≥ 1.5 g/dL from value at response) as well as for duration of response (days) defined as the time from onset of the first response to relapse. Duration of response will be evaluated within the whole 24 weeks period. Analysis will be performed on FAS and PP set.

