10.5.8 To estimate duration of erythroid response among responders treated with DFX+EPO

This analysis will include patients treated with DFX combined with EPO at baseline and patients who switch to DFX+EPO from EPO arm after 12 weeks. Descriptive statistics will be provided for responder patients for rate of relapse (decrease in Hb \geq 1.5 g/dL from value at response) as well as for duration of response (days) defined as the time from onset of the first response to relapse. Duration of response will be evaluated within the whole 24 weeks period for patients randomized to EPO+DFX and within week 13-24 for patients randomized to EPO at baseline and switched to combination therapy after 12 weeks. Analysis will be performed on FAS and PP set.

10.5.9 To assess iron parameters in patients randomized to EPO alone, DFX+EPO and in patients randomized to EPO alone and switched to DFX+EPO after 12 weeks

This analysis will include patients randomized either to EPO or DFX+EPO at baseline as well as patients who are non-responders to erythroid at week 12 in the EPO group switched to combination therapy. The time-course of serum ferritin and its absolute/relative changes from baseline will be summarized by descriptive statistics by visit and erythroid response. Data will be summarized on FAS and PP set.

Note: Patients randomized to EPO and not switching after 12 weeks to EPO+DFX, will consist of only responders.

10.5.10 To assess Hb parameters in patients in patients randomized to EPO alone, DFX+EPO and in patients randomized to EPO alone and switched to DFX+EPO after 12 weeks

This analysis will include patients randomized either to EPO or DFX+EPO at baseline as well as patients who are non-responders to erythroid at week 12 in the EPO group switched to combination therapy. The time-course of Hb and its absolute/relative changes from baseline will be summarized by descriptive statistics by visit and erythroid response. Data will be summarized on FAS and PP set.

[figure not shown]
Note: Patients randomized to EPO and not switching after 12 weeks to EPO+DFX, will consist of only responders.

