1.1 Document content

[figure not shown]
This Report and Analysis Plan (RAP) module describes the planned statistical methods for all efficacy and safety analyses for phase II study CICL670A2421 which is an open-label, phase II, randomized, pilot study to assess the effect in term of erythroid improvement of deferasirox (DFX) combined with erythropoietin (EPO) compared to EPO alone in patients with low- and int-1-risk myelodysplastic syndrome (MDS).

It is structured as:

- A draft of Section 9.7 (Statistical methods planned in the protocol and determination of sample size)
- A draft of Appendix 16.1.7 and 16.1.9 (Documentation of statistical methods) of the CSR.

It is written in future tense. It will be reviewed and updated (including conversion to past tense) for entry into the clinical study report after the analysis has taken place.

The shells for the in-text tables and figures, post-text tables, figures and listings, and the table of contents will be in Module 7. Programming specifications, including derivations and imputation dates will be given in Module 8.

2 Clinical Study Report Section 9.7 - Statistical methods planned in the protocol and determination of sample size

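### Duration of erythroid response has no rule for responses that do not end in relapse, and the visible SAP contains no duration analysis; read literally, only relapsers have a duration

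*Protocol*

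**What the plan says.** Duration of erythroid response is a secondary objective in the protocol summary and in Table 3-1, which states: "Duration of erythroid response is defined as the time from onset of the first response to progression/relapse".

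For EPO alone, Protocol 10.5.7 plans descriptive statistics for responders on two quantities. One is the "rate of relapse (decrease in Hb ≥ 1.5 g/dL from value at response"). The other is the "duration of response (days) defined as the time from onset of the first response to relapse". The window is given by "Duration of response will be evaluated within the whole 24 weeks period". For the combination, Protocol 10.5.8 repeats the definition and sets two windows: "Duration of response will be evaluated within the whole 24 weeks period for patients randomized to EPO+DFX and within week 13-24" for the patients who switched from EPO.

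Neither document names a censoring rule or a Kaplan-Meier estimate, or says what value a responder without relapse receives. SAP 4.6 sets no imputation as the default. SAP 4.3 closes ongoing events at the discontinuation date, but its examples are adverse events and concomitant medication.

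SAP 1.1 says the document "describes the planned statistical methods for all efficacy and safety analyses". SAP 2.9.2 then lists five secondary analyses: hematological response, erythroid response in switched patients, erythroid response on EPO alone, iron parameters and Hb parameters. Duration of response is not among them.

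**The concern.** A time that ends only at relapse exists only for patients who relapse. Follow-up stops at week 24, so a response that begins at week 4 can be seen for at most 20 weeks, and one that begins at week 12 for at most 12. Long responses are the ones least likely to end inside that window. If the definition is applied as written, the summary is built from the shortest responses and changes little with the true durability. Switched patients have a shorter window still, so a combined figure under 10.5.8 would mix groups with different maximum follow-up.

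At stake is whether the study can describe how long a response lasts, which is a stated objective in both arms.

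**Working it through.** **The plan's own figure.** The documents state no duration, relapse rate or event count, so there is nothing of this kind to reproduce.

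**Inputs from the documents.** Hb is measured at nominal days 14, 28, 42 (only after an EPO dose increase), 56, 84, 112, 140 and 168 (Protocol 7.2.2.4.1; SAP Table 4-1 and the text below it). The longest observable duration is 168 minus the onset day: 140 days for onset at day 28, 112 at day 56 and 84 at day 84. Switched patients change treatment at about day 84, so their first later Hb is day 112, which leaves at most 56 days (8 weeks).

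**Assumptions, not in the documents.** Relapse times are exponential with median m weeks. Onset is at weeks 2, 4, 8 and 12 with weights w = 0.1, 0.3, 0.3 and 0.3, so the remaining window is W = 22, 20, 16 and 12 weeks.

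**Formulas.**
- λ = ln 2 / m, and F(W) = 1 − exp(−λW).
- Share of responders relapsing in the window: p = Σ w F(W).
- Mean among relapsers: Σ w [F(W)/λ − W exp(−λW)] / p.
- Mean if ongoing responses are counted to week 24: Σ w F(W)/λ.

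For m = 26: λ = 0.02666 and F = 0.444, 0.413, 0.347, 0.274. Then p = 0.044 + 0.124 + 0.104 + 0.082 = 0.355 (unrounded terms). The bracketed terms are 4.41, 3.77, 2.58 and 1.56, with weighted sum 2.81, and 2.81 / 0.355 = 7.9 weeks.

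| True median (wk) | True mean (wk) | Relapse seen | Mean, relapsers only (wk) | Mean, ongoing counted to week 24 (wk) |
|---|---|---|---|---|
| 6 | 8.7 | 84% | 5.8 | 7.3 |
| 12 | 17.3 | 61% | 7.1 | 10.5 |
| 26 | 37.5 | 35% | 7.9 | 13.3 |
| 52 | 75.0 | 20% | 8.3 | 14.8 |

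**Check on the visit days.** This is a simulation of 400,000 responders per scenario, with onset at days 28, 42, 56 or 84 equally likely and relapse detected only at a scheduled Hb.

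| True median (wk) | True mean (d) | Mean, relapsers only (d) | Mean, ongoing counted to day 168 (d) | Kaplan-Meier median (d) |
|---|---|---|---|---|
| 6 | 61 | 54 | 63 | 56 |
| 12 | 121 | 63 | 82 | 98 |
| 26 | 263 | 68 | 98 | not reached (0.56 at day 140) |
| 52 | 525 | 71 | 106 | not reached (0.75 at day 140) |

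The true mean divided by the relapsers-only mean is 61/54 = 1.1, 121/63 = 1.9, 263/68 = 3.9 and 525/71 = 7.4. Visit spacing delays detection, which partly offsets the bias for short responses; in the continuous-time table the 6-week ratio is 8.7/5.8 = 1.5. For switched patients (onset at day 112 or 140) the relapsers-only mean is 35 to 37 days in every scenario.

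**Numbers available.** At the 40% reference rate of Protocol 10.8, 30 EPO patients give 12 responders. If 35% relapse, about 4 patients supply the duration.

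**Follow-up can end before relapse.** Three places describe the end of a response differently:
- Section 10.5.7: Hb down at least 1.5 g/dL from the value at response.
- Section 6.1.4: discontinuation from the study on a fall of at least 1.5 g/dL from best response, or on need for transfusion.
- Appendix 2: an Hb reduction of at least 1.5 g/dL, transfusion dependence, or a 50% fall in granulocytes or platelets.

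Best response is never below the value at response, so the discontinuation threshold is reached first or at the same time. As an illustration, take Hb 9.0 at baseline, 10.5 at response, 11.8 at best and 10.3 later. The fall from best is 1.5, so the patient leaves the study. The fall from the value at response is 0.2, so no relapse is recorded.

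**The case against.** The strongest reply is that no duration figure is planned for reporting. The visible SAP has no such analysis, parts of the SAP are not in the available text and may explain the omission, and Section 10 of the protocol leaves further details to the analysis plan. This stands against any claim that a biased result will be reported. It does not close the point, because the current protocol still lists the objective and SAP 1.1 claims full coverage of efficacy. Either the analysis is due and has no workable estimator, or it was dropped and the documents disagree.

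A reader might infer that the plan excludes non-relapsers. It does not say so: it promises statistics for responders. Exclusion is the literal consequence of the definition, and counting ongoing responses to the last visit is another possible reading. That reading also understates long responses, as the last column of the first table shows.

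A reader might also infer that the planned output cannot tell a short-lived from a lasting effect. That goes too far. The planned relapse rate would be about 35% and 20% for true medians of 26 and 52 weeks, and Hb by visit and by response is planned too. These outputs inform on durability, but they are not a duration.

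Finally, a constant relapse hazard is doubtful. Once Hb reaches 12 g/dL, "EPO will be stopped until the end of study", which may change the hazard. The computed sizes are therefore illustrative.

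**Conclusion.** The gap is real: there is no censoring rule in either document and no duration analysis in the visible SAP. The size is conditional. Under the stated assumptions the relapsers-only mean stays between about 6 and 8 weeks while the true median runs from 6 to 52 weeks. The bias is small if responses are short (54 against 61 days on the visit days at a 6-week median), roughly twofold at 12 weeks, and several-fold at 26 to 52 weeks. An unqualified statement that the duration will be far too short is not supported, because the documents give no true duration.

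This is a descriptive secondary endpoint in a pilot study with no planned test on duration, so the primary result is untouched. The point still deserves correction, because the definition as written yields a poor estimate and a standard method is available.

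**What to change.** In Protocol 10.5.7 and 10.5.8, and in a matching SAP section:

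1. Estimate duration by Kaplan-Meier from first response, censoring non-relapsers at their last Hb on or before week 24.
2. State how patients taken off study for an Hb fall of at least 1.5 g/dL from best response, or for transfusion, are counted. Censoring them is informative, so add a sensitivity analysis that counts them as relapses.
3. Reconcile Protocol 6.1.4, 10.5.7 and Appendix 2, which describe relapse differently.
4. Report the proportion still in response, with 95% CI, at 4, 8 and 12 weeks for the randomised arms. Show switched patients separately and only as far as their follow-up allows, about 8 weeks at most.
5. Keep the relapse rate as a companion figure.

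If the analysis has been dropped, say so with the reason, and make the protocol objectives and the SAP agree.

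The cost is wording and one standard procedure. With about 12 responders in the EPO arm the intervals will be wide and the median may be reported as not reached. Four-weekly visits also push the detected median up somewhat (56 against 42 days, and 98 against 84, in the check above).

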10.5.8 To estimate duration of erythroid response among responders treated with DFX+EPO

This analysis will include patients treated with DFX combined with EPO at baseline and patients who switch to DFX+EPO from EPO arm after 12 weeks. Descriptive statistics will be provided for responder patients for rate of relapse (decrease in Hb \geq 1.5 g/dL from value at response) as well as for duration of response (days) defined as the time from onset of the first response to relapse. Duration of response will be evaluated within the whole 24 weeks period for patients randomized to EPO+DFX and within week 13-24 for patients randomized to EPO at baseline and switched to combination therapy after 12 weeks. Analysis will be performed on FAS and PP set.

10.5.9 To assess iron parameters in patients randomized to EPO alone, DFX+EPO and in patients randomized to EPO alone and switched to DFX+EPO after 12 weeks

This analysis will include patients randomized either to EPO or DFX+EPO at baseline as well as patients who are non-responders to erythroid at week 12 in the EPO group switched to combination therapy. The time-course of serum ferritin and its absolute/relative changes from baseline will be summarized by descriptive statistics by visit and erythroid response. Data will be summarized on FAS and PP set.

Note: Patients randomized to EPO and not switching after 12 weeks to EPO+DFX, will consist of only responders.

10.5.10 To assess Hb parameters in patients in patients randomized to EPO alone, DFX+EPO and in patients randomized to EPO alone and switched to DFX+EPO after 12 weeks

This analysis will include patients randomized either to EPO or DFX+EPO at baseline as well as patients who are non-responders to erythroid at week 12 in the EPO group switched to combination therapy. The time-course of Hb and its absolute/relative changes from baseline will be summarized by descriptive statistics by visit and erythroid response. Data will be summarized on FAS and PP set.

[figure not shown]
Note: Patients randomized to EPO and not switching after 12 weeks to EPO+DFX, will consist of only responders.

10.5.11 Safety objectives

Analysis will be done on safety set.

10.5.11.1 Analysis set and grouping for the analyses

The overall study period will be divided into three mutually exclusive segments:

1. pre-treatment period: from day of patient's informed consent to the day before first dose of study medication
2. on-treatment period: from day of first dose of study medication to 30 days after last dose of study medication
3. post-treatment period: starting at day 30+1 after last dose of study medication.

The reporting of AEs and AEs of special interest will be reported in the following periods based on the treatment received as follows:

- For patients receiving EPO during the first 12 weeks and for those continuing with EPO after 12 weeks (no switching to EPO+DFX arm), the safety data will be reported based on the corresponding treatment group: EPO. The safety data will be reported in period 1-12 weeks, 13-24 weeks and 1-24 weeks.
- For patients receiving EPO+DFX from week 1 and continuing with EPO+DFX after 12 weeks or with DFX alone after 12 weeks, the safety data will be reported based on the corresponding treatment EPO+DFX. The safety data will be reported in period 1-12 weeks and 1-24 weeks.
- For patients receiving EPO alone and switched to EPO+DFX after 12 weeks of treatment, the safety data will be reported only in period 13-24 weeks.

10.5.11.2 Adverse events (AEs)

Summary tables for adverse events (AEs) will include only AEs that started or worsened during the on-treatment period, the **treatment-emergent** AEs. However, all safety data (including those from the pre and post-treatment periods) will be listed and those collected during the pre-treatment and post-treatment period are to be flagged.

[figure not shown]
The incidence of treatment-emergent adverse events (new or worsening from baseline) will be summarized by system organ class and or preferred term, severity (mild/moderate/severe), type of adverse event, relation to study treatment by treatment group.

Deaths reportable as SAEs and non-fatal serious adverse events will be listed by patients and tabulated by type of adverse event and treatment group.

10.5.11.3 Laboratory abnormalities

All laboratory values will be converted into SI units and the severity grade calculated using the low/normal/high classifications based on laboratory normal ranges and for selected parameters by notable/extended ranges.

The following summaries will be generated separately for hematology, biochemistry and urinary laboratory tests:

- shift tables using normal/notable/extended ranges to compare baseline to the worst on-treatment value
- listing of all laboratory data with values flagged to show the corresponding normal/notable/extended ranges.

For each hematology/iron metabolism parameter, observed values (and changes from baseline) will be summarized by descriptive statistics (n, mean, standard deviation, minimum, lower quartile, median, upper quartile and maximum).

Creatinine clearance will be estimated using the Cockcroft-Gault equation will be displayed using relative change from baseline by categories.

10.5.11.4 Other safety data

Data from electrocardiogram, vital signs, ocular and auditory examination will be listed, summarized and flagged as appropriate by treatment group.

Any significant findings after start of study will be documented as adverse events and reported as such.

10.5.12 Resource utilization

Not applicable.

10.5.13 Patient-reported outcomes

Not applicable.

10.7 Interim analysis

Not applicable.

10.8 Sample size calculation

This is a pilot study which plans to enroll approximately 60 patients considering site capabilities. The sample size in a pilot study is based on the pragmatics of recruitment and the necessities of examining feasibility (Leon et al, 2011). Hence no formal sample size calculation based on primary endpoint assumptions is performed.

However to give an idea regarding primary endpoint analysis, for a given number of 60 patients, under scenarios, where considering a minimal detectable differences of 20%, 30% and 40% assuming a reference response rate of 40% at 5% level of significance gives a 95% Agresti-Caffo confidence interval of (-0.04, 0.44), (0.068, 0.53) and (0.18, 0.62).

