6.5.2 Treatment assignment or randomization

[figure not shown]
Patients will be assigned to one of the 2 treatment arms ([Section 4.1](#) and [Section 6.1](#)) in a ratio of 1:1.

The randomization numbers will be generated using the following procedure to ensure that treatment assignment is unbiased and concealed from patients and investigator staff. A patient randomization list will be produced by the Interactive Web Response Technology (IWR) provider using a validated system that automates the random assignment of patient numbers to randomization numbers. These randomization numbers are linked to the different treatment arms.

Prior to dosing, all patients who fulfill all inclusion/exclusion criteria will be randomized via IWR to one of the treatment arms. The investigator or his/her delegate will log on to the IWR and confirm that the patient fulfills all the inclusion/exclusion criteria.

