2.11 CSR Section 9.7.2: Sample size and power considerations

This is a pilot study that was planned to enroll approximately 60 patients considering site capabilities. No formal sample size calculation based on primary endpoint assumptions is performed.

However to give an idea regarding primary endpoint analysis, for a given number of 60 patients, under scenarios, where considering a minimal detectable differences of 20%, 30% and 40% assuming a reference response rate of 40% at 5% level of significance gives a 95% Agresti-Caffo confidence interval of (-0.04, 0.44), (0.068, 0.53) and (0.18, 0.62).

Clinical Development

ICL670

CICL670A2421

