6.2 Agresti-Caffo CI for difference in proportions

The Agresti-Caffo confidence limits for the risk difference are computed as:

$$\tilde{d} \pm (z_{\alpha/2} \times \text{s.e}(\tilde{d}))$$

where $\tilde{d} = \tilde{p}_1 - \tilde{p}_2$, $\tilde{p}_i = (n_{i1} + 1)/(n_{i.} + 2)$,

$$\text{se}(\tilde{d}) = \sqrt{\tilde{p}_1(1 - \tilde{p}_2)/(n_{1.} + 2) + \tilde{p}_2(1 - \tilde{p}_1)/(n_{2.} + 2)}$$

and $z_{\alpha/2}$ is the $100(1 - \alpha/2)$ percentile of the standard normal distribution.

That is: $\tilde{p}_1 = (n_{11} + 1)/(n_{1.} + 2)$ and $\tilde{p}_2 = (n_{22} + 1)/(n_{2.} + 2)$

	Column 1	Column 2	Total
Row 1	n_{11}	n_{12}	$n_{1.}$
Row 2	n_{21}	n_{22}	$n_{2.}$
Total	$n_{.1}$	$n_{.2}$	n

The Agresti-Caffo interval adjusts the Wald interval for the risk difference by adding a pseudo-observation of each type (success and failure) to each sample. See Agresti and Caffo (2000) for more information.

This CI calculation is available in SAS Version 9.3 using the CL=AC options as follows:

```
ods select PdiffCLs;  
ods output PdiffCLs=ciac;  
proc freq data= dataset;  
    tables group*response /riskdiff (CL=AC);  
run;
```

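### The three illustrative 95% Agresti-Caffo intervals in Protocol 10.8 and SAP 2.11 are not Agresti-Caffo intervals, and the 20-point difference labelled minimal detectable has an interval that includes 0

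*Protocol*

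**What the plan says.** Protocol 10.8 sets the sample size on practical grounds: "This is a pilot study which plans to enroll approximately 60 patients considering site capabilities". It adds: "Hence no formal sample size calculation based on primary endpoint assumptions is performed". As an illustration for the primary endpoint, it then lists three scenarios and says that they "gives a 95% Agresti-Caffo confidence interval of (-0.04, 0.44), (0.068, 0.53) and (0.18, 0.62").

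SAP 2.11 repeats the intervals and introduces the scenarios in the same way, as "considering a minimal detectable differences of 20%, 30% and 40% assuming a reference response rate of 40% at 5% level of significance".

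SAP 6.2 describes the Agresti-Caffo interval as a Wald interval modified by "adding a pseudo-observation of each type (success and failure) to each sample". It centres the interval on the difference of the adjusted proportions. For the final analysis it gives the SAS statement "tables group*response /riskdiff (CL=AC").

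**The concern.** An Agresti-Caffo interval is pulled towards 0 because one success and one failure are added to each arm. It should therefore be centred a little below a positive raw difference. The printed intervals have midpoints of 0.200, 0.299 and 0.400, which are the raw differences to rounding. That suggests a different calculation.

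Separately, a difference called minimal detectable at the 5% level should have a 95% interval that excludes 0. The one printed for 20 points runs from -0.04 to 0.44.

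This sentence is the plan's only statement of precision for the primary comparison. If it is wrong, readers are shown limits that the named method would not return for those data, and they could take 20 points as the smallest difference the trial can demonstrate. SAP 1.1 says the document is a draft of CSR Section 9.7, so the figures would also pass into the study report.

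**Working it through.** **Inputs**

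- 60 patients (Protocol 10.8), allocated 1:1 (Protocol 6.5.2), so 30 per arm.
- Reference rate 40%, i.e. 12/30 on EPO alone (Protocol 10.8).
- Differences of 20, 30 and 40 points, i.e. 18/30, 21/30 and 24/30 on DFX+EPO.
- 95% two-sided, z = 1.96.

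**Reproducing the printed figures**

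Use unadjusted proportions p1 and p2 = 0.40, with 32 (30 + 2) in each denominator:

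(p1 − p2) ± 1.96 × √[(p1(1−p1) + p2(1−p2))/32]

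- 20 points: 0.20 ± 1.96 × √[(0.24 + 0.24)/32] = 0.20 ± 0.2400 → (-0.0400, 0.4400)
- 30 points: 0.30 ± 1.96 × √[(0.21 + 0.24)/32] = 0.30 ± 0.2324 → (0.0676, 0.5324)
- 40 points: 0.40 ± 1.96 × √[(0.16 + 0.24)/32] = 0.40 ± 0.2191 → (0.1809, 0.6191)

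These match every printed digit. The 2 was added to the denominators, but the 1 was not added to the number of successes.

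**The Agresti-Caffo intervals**

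p̃ = (x+1)/32, d̃ = p̃1 − p̃2, interval d̃ ± 1.96 × √[(p̃1(1−p̃1) + p̃2(1−p̃2))/32]. The EPO arm has p̃2 = 13/32 = 0.40625.

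| Scenario | p̃1 | d̃ | Half-width | Agresti-Caffo | Printed |
|---|---|---|---|---|---|
| 18/30 vs 12/30 | 19/32 | 0.1875 | 0.2407 | (-0.053, 0.428) | (-0.04, 0.44) |
| 21/30 vs 12/30 | 22/32 | 0.2813 | 0.2340 | (0.047, 0.515) | (0.068, 0.53) |
| 24/30 vs 12/30 | 25/32 | 0.3750 | 0.2224 | (0.153, 0.597) | (0.18, 0.62) |

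Printed minus Agresti-Caffo:

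- lower limits: 0.013, 0.021, 0.027
- upper limits: 0.012, 0.015, 0.023

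**Other readings tried**

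- Ordinary Wald with 30 in the denominators: (-0.048, 0.448), (0.060, 0.540), (0.174, 0.626).
- The standard error as literally printed in SAP 6.2, which has the cross terms p̃1(1−p̃2) and p̃2(1−p̃1): (-0.062, 0.437), (0.028, 0.535), (0.117, 0.633).
- The expanded p̃2 in SAP 6.2 taken literally, with n22 (non-responders) in place of n21: (-0.241, 0.241), (-0.140, 0.328), (-0.035, 0.410).
- Continuity-corrected Wald, pooled standard error, Newcombe, Miettinen-Nurminen, a 90% level, and Agresti-Caffo with unequal arms of 10 to 120.

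None gives all three printed intervals.

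**The minimal detectable label**

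Both the printed and the Agresti-Caffo interval for 20 points include 0. With 12/30 on EPO alone:

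- 19/30 gives (-0.020, 0.458)
- 20/30 gives (0.013, 0.487)

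So the smallest observed difference whose interval excludes 0 is 20/30 − 12/30 = 26.7 points.

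For context, exact binomial enumeration with 30 per arm and a true EPO rate of 40% gives the probability that the Agresti-Caffo interval lies wholly above 0:

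| True difference | Probability |
|---|---|
| 20 points | 35% |
| 30 points | 66% |
| 40 points | 90% |

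No target power is stated in either document. If 80% were taken as a conventional assumption, it would be reached at about 35 points (0.802).

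**The case against.** The strongest reply is that nothing in the plan depends on these intervals. The sample size rests on recruitment and feasibility, both documents disclaim a formal calculation, no interim analysis is planned, and the primary analysis is estimation with no success threshold. The limits move by 1 to 3 points and no scenario changes sides of 0. All of that stands, and it is why the point is minor.

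A second reply is that minimal detectable is applied to three values at once, so it can only be loose wording for assumed differences, and the printed lower limit of -0.04 already warns the reader. That is a fair reading and makes this part a wording correction. The label still contradicts the interval beside it. The power figures above are likewise context, since the pilot sets no power target.

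A third reply is that SAP 6.2 is not a clean benchmark, because its printed standard error and its expanded p̃2 both contain slips. This is true. The corrected figures follow its verbal description, its general definition of the adjusted proportion and the usual Agresti-Caffo variance. It does not rescue the printed intervals, because no reading of SAP 6.2 produces them.

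Finally, Protocol 12.1 requires a written, approved amendment for any protocol change. That bears on timing and does not make the figures right.

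**Conclusion.** The concern holds, as a minor point. The three printed intervals are Wald-type intervals around the raw difference with 32 in the denominators, and they are mislabelled as Agresti-Caffo. All six limits are too high, which favours DFX+EPO, by 1.2 to 2.7 percentage points. The 20-point difference is called minimal detectable although its interval includes 0 before and after correction.

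This rests on 30 patients per arm and exactly 12/30 responders on EPO alone, both of which follow from the documents' own inputs. Sample size, conduct and the final analysis through the SAS option are not affected.

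**What to change.** In Protocol 10.8 and SAP 2.11, replace the illustrative sentence with text such as: *With 60 patients (30 per arm) and an observed response rate of 40% (12/30) on EPO alone, observed differences of 20, 30 and 40 percentage points correspond to 95% Agresti-Caffo intervals of (-0.05, 0.43), (0.05, 0.52) and (0.15, 0.60).* Drop the minimal detectable label. Drop the reference to the 5% significance level as well, since the confidence level already conveys it. Optionally, add the probability that the interval lies above 0 for true differences of 20, 30 and 40 points (about 35%, 66% and 90%).

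Correct the standard error and the expanded p̃2 in SAP 6.2 at the same time; otherwise the new figures will disagree with the formula printed there.

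The cost is wording only, and the figures become slightly less favourable. The SAP can be changed directly and the correction carried into the CSR. The protocol sentence can wait for the next amendment made for another reason.
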